**D. Study Design/Approach.** The study will involve 22 middle schools (12 in SC, 10 in MD) in a cluster-RCT, with all schools receiving the Wellness intervention and half of the schools (6 in SC, 5 in MD) randomized to receive enhanced intervention including the two SEs (Partnership). Stratified random assignment of schools to the Wellness Group or the Partnership Group will be conducted. We will then use validated procedures (23, 24) to further stratify schools within each state. We will construct a composite inflate-suppress score derived from school data on rurality, average number of students per grade, percent white, percent receiving free/assisted lunch, and average school test performance. Rurality within the two study sites will be operationalized by using a federally developed classification system used by The US Census Bureau (i.e., a 9-point, "Rural-Urban Continuum"). The coding scheme will distinguish three metro county categories based on population size, and six non-metro county categories based on degree of urbanization, as well as adjacency to other areas and metro proximity. Per operationalization of rurality in the federally-based coding continuum, we can confirm that the SC study sites contain county classifications of rural and suburban, while the MD site is exclusively urban. We will separate this composite into three strata and randomly assign schools from these strata to receive either the Wellness Group or the Partnership Group.

In the 5-year longitudinal design, Year 1 will involve administrative start up, collection of pre-assessments and intervention launch; Years 1-4 will involve intervention versus comparison while participants are in 6th through 8th grades. Year 5 will involve analyses and dissemination. A comprehensive implementation manual will guide the study and will be updated and improved regularly through active guidance of a Stakeholder Advisory Board (SAB, see Tables 3 and 4 in Appendix). The SAB will provide significant input as this manual is developed during the study start-up period from January through July, 2019, and progressively improved through study duration (see Gantt chart in Figure 1 of the Appendix for a review of all study activities in time).

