Please note, we will analyze data related to services received and outcomes for students of varying race/ethnicity as a supplemental, exploratory aim. Because of increased attention to cultural issues, it is possible that the Partnership intervention may have additional benefits in reducing disparities in services and outcomes for youth of color. Should findings indeed point to benefits of the Partnership intervention, these will be integrated into our dissemination plan and help to fuel critically important future research.

**Study Population and Setting.** Intervention will begin during the 2019-20 school year, and it will continue through the 2022-2023 school year. The study sample will include students from 22 middle schools, with 12 schools from SC and 10 from MD. One mental health center in each state will work with the study, with these mental health centers already having established relationships with the middle schools, with clinicians placed in these schools .7 FTE or 3.5 days per week. In MD, the site will be [REDACTED] (urban), with one school district and all 10 middle schools coming from this

PRINCIPAL INVESTIGATOR: [name]

site. In SC, the site will be [REDACTED] County (suburban and rural). Letters of support from mental health center leaders and the two school districts are included, reflecting the strong partnerships already established between the mental health centers and these districts.

Utilizing the demographic information available from each site's state Department of Education database, participating schools are predominately male (52%) and White (45%), followed by Black/African American (37%), Asian and Multiracial (3%), and less than one percent American Indian and Pacific Islander, with 12% identifying as Hispanic. Current prevalence estimates (2,14) predict that 20% of youth will meet criteria for a more serious EB problem. Due to random school assignment to condition, we predict these percentages will be evenly split across Wellness and Partnership.

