As presented above, critical demographic factors will be assessed to investigate whether members of underrepresented groups present unique needs for services. Participant subgroups that will be further evaluated will include those varying based on mental health diagnosis, gender, race/ethnicity, and sociodemographic characteristics including income status, urban-rural-suburban status, and neighborhood levels of crime and violence. Initial analyses will be conducted to determine whether there are significant differences in primary outcomes of interest for subgroups compared to the overall sample. In instances where significant differences are found for a subgroup, interaction effects will be examined within a two-level HLM framework (see above) to further explore subgroup differences.

**Recruitment Plan.** School enrollment of each participating school was retrieved at the SC and MD state educational databases to determine the average middle school population is 600 across participating schools. In Year 1, around 12,000 students will attend the 20 study schools with an estimated additional 8,000 students entering study schools as 6th graders in Years 2 and 3, totaling 20,000 potential participants during the three-year implementation phase.

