**Site Selection.** Proposed study sites were selected based on factors related to feasibility as well as their potential for providing a representative patient sample. Both the [REDACTED] Mental Health Center ([REDACTED] MHC) and the CSMH, have long histories of collaboration with investigators of this study. This existing relationship provides many benefits in avoiding common barriers to implementation. The two sites offer complementary demographics with CSMH serving youth who are primarily urban and African American, while [REDACTED] MHC serves a suburban and rural youth population that is more diverse racially and ethnically, and both sites serve low and middle income families, allowing us to evaluate for a variety of outcomes in subgroup populations. Additionally, incorporating the two interventions into routine SBH practices will facilitate findings that are immediately applicable to real world contexts.

PRINCIPAL INVESTIGATOR: [name]

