## PROTECTION OF HUMAN SUBJECTS.

Twenty-two middle schools (12 in South Carolina and 10 in Maryland) will participate in a cluster-randomized controlled trial with stratified random assignment used to assign schools to the Wellness Group or the Partnership Group for a 5-year longitudinal study. These schools will be from two school districts including urban and suburban (MD), and rural and rural/suburban (SC) sites. Schools will utilize existing referral processes for identifying students in need of Tier 3 services. Critical demographic factors will be assessed to investigate whether members of underrepresented groups present a unique need for services. It is estimated that over the course of the study, approximately 4,000 students/families will be eligible to participate, and about 30% will provide assent/consent. Thus, student participants will include an estimated 1,225 youth (approximately 612 in each condition) across 12 middle schools in South Carolina and 10 middle schools in Maryland. Students may participate in the sixth through eighth grades. The two interventions being evaluated are systemic and will be a part of normal educational or therapeutic treatment that the students would ordinarily receive. Students receiving Tier 3 services and their parents will be consented to provide assessment batteries at in-take and every three months during treatment. For students not receiving treatment with a clinician, researchers will implement an opt-out procedure, informing students and their parents that researchers will be collecting de-identified school records and climate survey on students in the school and that they may choose to opt out if they desire. Significant collaboration with the SAB will occur to ensure the protection of participants' privacy and confidentiality.

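### With a county-level rurality code and conflicting site descriptions, urban versus non-urban cannot be separated from state, and rural versus suburban may not be testable

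*Combined protocol and SAP*

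**What the plan says.** All references are to the combined protocol and SAP.

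- **Section D, Study Design/Approach.** Rurality is a nine-point federal code whose categories belong to counties: "The coding scheme will distinguish three metro county categories based on population size, and six non-metro county categories based on degree of urbanization". It is one of five inputs to a "composite inflate-suppress score derived from school data on rurality, average number of students per grade, percent white" and two further school variables. The composite serves to "further stratify schools within each state": "We will separate this composite into three strata and randomly assign schools from these strata". The section then says it can confirm that the South Carolina sites include rural and suburban county classes and that Maryland is urban only.
- **Study Population and Setting.** All 10 Maryland schools come from one district, labelled urban. For the other state: "In SC, the site will be [REDACTED] County (suburban and rural". Two school districts are mentioned in all.
- **Subgroups, same section.** Factors to be evaluated include "income status, urban-rural-suburban status, and neighborhood levels of crime and violence". Where a subgroup differs, interactions are examined in the two-level model. No coding is given for the urbanicity factor. Race/ethnicity is a supplemental, exploratory analysis.
- **Analytic Plan.** Site (South Carolina versus Maryland) enters as a covariate. No arm-by-site term is specified.
- **Site Selection.** The two sites are described as complementary, with "CSMH serving youth who are primarily urban and African American" and the South Carolina centre serving suburban and rural youth.
- **Protection of Human Subjects.** The schools come from "two school districts including urban and suburban (MD), and rural and rural/suburban (SC) sites".

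**The concern.** A county code cannot distinguish schools inside one county. One named South Carolina county therefore does not fit with two county classes in that state, and the two accounts of Maryland disagree as well. The reader cannot tell how many values the rurality variable takes in either state.

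This matters most for the subgroup analysis. The states differ in much besides urbanicity: mental health centre, school district and senior trainers. From spring 2020 the Partnership teams met jointly across states, and no such change is described for Wellness. A difference in Partnership effect between states is therefore plausible for reasons unrelated to urbanicity. If urban simply means Maryland, the interaction test cannot tell these explanations apart, yet its label would credit urbanicity. Site Selection uses this contrast to justify the choice of sites, so readers will look for the result.

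A milder form of the problem affects race/ethnicity and any other student characteristic whose distribution differs by state. With site only as a main effect, part of a state difference in treatment effect can load onto the characteristic-by-arm term.

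**Working it through.** The plan gives no figure to reproduce on this point. The check is structural, with two supporting calculations.

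**1. What can be estimated.** Take 22 schools (12 South Carolina, 10 Maryland), with Maryland urban only as section D states. Then urban = 1 − SC for every school.

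| Rurality codes in SC | Columns: intercept, site, rurality | Rank | Columns with arm and interactions | Rank |
|---|---|---|---|---|
| One | 3 | 2 | 6 | 4 |
| Two (6/6 or 3/9 split, illustrative) | 4 | 3 | 8 | 6 |

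With one code, rurality and site are the same variable. With two, one rurality contrast is estimable: rural versus suburban among the 12 South Carolina schools. In both cases urban versus non-urban is aliased with site.

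**2. Stratification.** If a state has one code, each of its schools' composites becomes c_j = b_j + k, where b_j is the contribution of the other four inputs and k is a constant. Ranks within the state do not change. In 2,000 simulated sets of the other four inputs, the within-state strata were identical with and without rurality every time. The input is idle, not harmful.

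**3. Race-by-arm leakage.** Inputs from the plan: 37% Black/African American across participating schools, 12 and 10 schools, and 1225/22 ≈ 56 students per school. Assumptions: equal school sizes; Maryland share m between .51 and .75 (the plan says only that it is the primary group there); a state difference in Partnership effect δ of .2 to .4 SD; no true race difference in effect; ICC .06. The plan states no ICC. A value of about .059 reproduces its minimum detectable effect of .29 if the 30% of variance explained applies at both levels, with 19 degrees of freedom: (2.093 + .861) × √[.059×.7/5.5 + .941×.7/(5.5×55.7)] = 2.954 × .0983 = .29.

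South Carolina share = (.37 − (10/22)m)/(12/22): m = .51 gives .253, .60 gives .178, .65 gives .137, .75 gives .053.

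The expected random-intercept estimate is (X′V⁻¹X)⁻¹X′V⁻¹μ, where μ = δ·arm·site and X holds intercept, arm, site, race and arm×race.

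| m | Bias, δ = .2 | Bias, δ = .4 | False-positive rate | SE without → with arm×site |
|---|---|---|---|---|
| .51 | .013 | .026 | 5–6% | .118 → .119 |
| .60 | .023 | .047 | 5–7% | .124 → .127 |
| .65 | .029 | .059 | 6–7% | .129 → .134 |
| .75 | .054 | .108 | 7–11% | .148 → .164 |

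Adding arm×site, or centring race within school, takes the bias to zero. Simulations of the same set-up gave roughly .02–.11 SD without the term and .01 SD or less with it. The size depends on the ICC: across the same cells it is .022–.161 SD at ICC .03 and .008–.074 SD at ICC .10.

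**4. Precision of rural versus suburban within South Carolina.** Six schools per arm split evenly (assumed) leave three per cell. With ICC .06, 56 students per school and 30% of variance explained, SE = √[4 × .7 × (.06 + .94/56)/3] = √.0717 = .268. With 8 degrees of freedom, the interaction detectable at 80% power is (2.306 + .889) × .268 ≈ .86 SD.

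**The case against.** A reader might infer that rurality is constant in both states, so that the whole urban-rural-suburban result is just Maryland versus South Carolina. The documents do not establish that. Section D says South Carolina has two classes. The single-county line is partly redacted; its singular wording is a fair basis for reading one county, but it creates a conflict and does not settle it. The subgroup list does not say that it reuses the county code, and it sits beside a neighbourhood-level factor, so a finer measure may be intended. With two South Carolina classes, rural versus suburban can be estimated.

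A reader might also infer that the randomisation was impaired. It was not: a constant input leaves the within-state strata untouched, and the other four inputs can still vary by school. Schools have already been assigned, so changing the rurality code in section D now would misdescribe what was done.

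The race figures rest on shares and a state difference that the plan does not give. A Maryland share near the low end fits better with Site Selection calling the South Carolina population more diverse, and there the false-positive rate is close to nominal. These analyses are exploratory and affect no primary aim.

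The Analytic Plan's k-1 sensitivity analysis, if site means state, would fit each state separately and expose a state difference. It still could not attribute that difference to urbanicity.

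All of this limits the point. It does not remove the aliasing of urban with Maryland, which holds however South Carolina is coded, so long as Maryland is urban only.

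**Conclusion.** The concern holds in limited form. Section D conflicts with Study Population and Setting on South Carolina, and with Protection of Human Subjects on Maryland. If Maryland is urban only, the aliasing of urban versus non-urban with state is complete, and the interaction would be reported under the wrong name. Whether rural versus suburban can be tested depends on which measure the subgroup analysis uses: with the county code and a single South Carolina code, it cannot.

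The race-by-arm consequence is modest, about .01–.11 SD at ICC .06 with false-positive rates of about 5–11%. It is conditional on the assumed Maryland share, state difference and ICC. Neither the primary comparison nor the validity of the allocation is in question.

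**What to change.** 1. Reconcile section D, Study Population and Setting and Protection of Human Subjects on the number of South Carolina counties and on whether Maryland is urban only.
2. Leave section D's account of the completed randomisation as it was carried out. Add a note that the rurality input does not separate schools within a state that has one code.
3. For the subgroup analysis, define urbanicity by a school-level locale classification (address or attendance zone). Test rural versus suburban moderation only among the 12 South Carolina schools and describe it as low precision. Report the Maryland–South Carolina contrast as state.
4. In the race/ethnicity and other moderator models, add an arm-by-site term or centre student characteristics within school.

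The cost is 22 school look-ups, one model term and slightly wider moderator intervals: in the table above, the standard error rises by about 1% at the lowest Maryland share and 11% at the highest (.164/.148). The within-South Carolina test will detect only large differences, so its value lies mainly in labelling the result correctly.

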*Engagement in Conducting the Study.* During project start up, the SAB will identify an informal project name and logo that will be used on study materials, a website, ways to most effectively communicate with patients, families and stakeholders and ways for them to access information and materials from the study. The SAB will review parent/guardian recruitment letters and provide input to assure understandability and sensitivity of the language used, and will improve overview materials that will be used when orienting school and mental health staff to study procedures/resources. Throughout implementation, the SAB will be provided with frequent progress updates including information on successes and challenges encountered related to recruitment, implementation of both interventions and data collection. The SAB will review preliminary (aggregated) data reports and assist in interpreting them to adjust the research strategy as needed. In addition, data will be disaggregated for analysis of service receipt and impacts for groups varying on grade level, age, gender, race/ethnicity, and special education status. If disparities in service receipt or outcomes are identified, the SAB will guide the study team in making adjustments to assure responsiveness in services. The SAB will also identify additional research questions to be pursued and will be encouraged to participate actively in supplementary studies. Additionally, during in-person meetings, we will seek feedback from the SAB on their level of engagement in the study and ways to improve engagement.

For the Partnership condition, two family advocates serving on the SAB (1 in MD and 1 in SC) will co-lead training for clinicians, school staff and selected parent leaders from each of the 11 schools at the beginning of each year, with emphasis on family partnerships and cultural humility. Parent leaders will be carefully selected, assuring they are racially representative of their school to mitigate barriers of mistrust from underserved and minority populations. Parent leaders will be compensated for the time spent to collaborate with fellow parents and school staff to communicate about and promote the study, as well as perform outreach to minority populations to increase their access to effective SBH services, as well as other programs and services available in the school and community.

PRINCIPAL INVESTIGATOR: [name]

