
2. *Stakeholder Enhancements (Partnership) Intervention*. The Partnership intervention will involve all of the above components of the Wellness intervention, and the two additional components identified by patients and stakeholders from the recent PCORI award and from relevant research literature. The Wellness intervention will focus on these two evidence-based enhancements working together in a school-wide strategy focused on clinicians working actively on school teams and assisting in promotion/prevention -Tier 1, early intervention - Tier 2, and treatment -Tier 3 within the multi-tiered system of support (MTSS). Clinicians will actively participate in the MTSS to help improve school culture, and enable effective implementation of all intervention elements including SEs. In each of the 11 Partnership schools, a parent leader, and school-employed mental health professional (e.g., school psychologist, counselor) will be assigned to work with the clinician and implementation team, one day per week through resources allocated from the grant. The two SEs will be: Mental Health Literacy and Stigma Reduction. To enhance mental health literacy and focus purposefully on reducing the stigma of seeking SBH services, a program called The Guide, developed in Canada and beginning to be used in the US and other nations, will be used (see [www.teenmentalhealth.org/curriculum](http://www.teenmentalhealth.org/curriculum)). The Guide is a teacher-delivered mental health curriculum for middle and high schools. Teachers, as supported by clinicians and parent leaders will deliver the program, which includes didactics, interactive classroom activities, and experiential learning. The Guide consists of modules focused on stigma and reducing it, understanding mental health, mental health challenges, and seeking help/finding support, with positive outcomes of increased mental health knowledge and reduced stigma for participating students (43,44). The program is being used throughout Canada, in Washington State, and in a number of other countries, and it has strong feasibility and acceptability data, helping to support its growth and sustainability in

PRINCIPAL INVESTIGATOR: [name]

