
Enhancing Family-School-Mental Health Partnerships. The Partners for Change Outcome Management System (PCOMS) has been used for more than two decades to enhance patient involvement in mental health services and to improve the therapeutic alliance between patients and clinicians (see 45-47). Foundational to the program are two brief measures: The Outcome Rating Scale (ORS, 46) and the Session Rating Scale 3.0 (SRS, 47). The ORS measures progress in EB symptoms and social relationships (completed at the beginning of the session) and the SRS measures therapeutic alliance including quality of the relational bond, and agreement on treatment goals and methods (completed at the end of the session). Both scales take less than a minute to complete and score and are available for free online at [www.talkingcure.com](http://www.talkingcure.com). The PCOMS program helps to promote dialogue on how therapy is proceeding, increases chances for active student/parent input, and helps to assure that both groups are in sync with treatment plans and progress. In addition to the PCOMS system, SBH efforts in Partnership schools will be enhanced by active participation of the parents on MTSS teams, which will also receive regular guidance, ideas and resources from the study's SAB (see Engagement Plan). Please note that family-school-mental health partnerships will also be enhanced by ongoing involvement and guidance by the family advocate at each site, and parent leader at each of the 11 Partnership schools.

PRINCIPAL INVESTIGATOR: [name]

In addition, in each of the 11 Partnership schools, clinicians and MTSS teams will conduct trainings on both Partnership Group enhancements, as appropriate. Clinicians and MTSS teams should leverage grade-level meetings to provide trainings and information as appropriate for each school environment.

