The second avenue of recruitment will be for students receiving Tier 3 treatment services. These students/parents will be consented using electronic consent (e-consent) in REDCap, with the consent form appended at the beginning of the survey. Participants and their parents will be required to go through the informed consent process and digitally sign the consent form using a mobile tablet device before proceeding into the survey questionnaire. MUSC has successfully piloted e-consent in REDCap with other IRB approved research studies. Given challenges with parents' ability to attend meetings at the school to complete the enrollment process, the study team developed protocol to allow for consent to be gained via phone and intake to be completed remotely via phone or computer. This flexibility allows enrollment to continue, and not be hampered by potential transportation or financial constraints that may otherwise prevent low-income families from participating. Additionally, as result of the COVID-19 crisis, procedures were developed to allow students to assent into the study via telephone or video conference. Students and parents may provide assent/consent via phone, after viewing consent materials and having the opportunity to ask questions of the clinician. Intake assessments can be completed verbally (via phone or video conference) or a link to complete surveys online may be sent via email or directly through the REDCap program by the clinician or research manager.

PRINCIPAL INVESTIGATOR: [name]

Based on current prevalence data, twenty percent (2,14) of students are expected to present with mental health challenges (n= 4,000). Of these students, based on the experience in similar studies the research team estimates that 30% will consent to participate representing the recruitment goal of 1,225 students by the end of the 2022-23 academic year. The rate of recruitment will be higher initially due to enrollment of students currently receiving services, however, over the course of the study an average of 35 students per month (during the academic year only, or four years times 9 months for 36 months total) will be enrolled. Note: significant changes to enrollment targets have been made during this project largely related to the unanticipated and unprecedented impact of the COVID-19 pandemic which temporarily closed school buildings and changed mental health care services starting in March 2020.

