There are essentially six classes of student participants, with groups based on grade level at the start of the intervention vs. comparison (IvC) period of the study, which begins in the 2019-20 school year. There is a four-year IvC period, 2019-20, 2020-21, 2021-22, and 2022-23. Group A will be in the 6th grade in 2019-20, with students experiencing 1-3 years of services in this time interval. These students could have received services in 6th, 7th and/or 8th grades during the IvC period. Group B will be in the 7th grade in 2019-20, with students experiencing 1-2 years of services in this time interval. These students could have received services in 7th and/or 8th grades during the IvC period. Group C will be in the 8th grade in 2019-20, with students experiencing 1 year of services in this time interval. Group D will enter the study in 6th grade in 2020-21. Group E will enter the study in 6th grade in 2021-22. Group F will enter the study in 2022-2023 while in 6th grade.

*Identifying eligible participants.* Participants already receiving treatment and those newly referred for services will be eligible to participate and recruited by their SBH clinician. Throughout the implementation phase (years 1-4) each school will use their existing referral process to identify students in need of treatment which will be followed up and confirmed by the SBH clinician prior to enrolling them in the study.

*Overcoming barriers to enrollment.* In addition to our successful experiences with the opt-out procedure to be used for stream 1 data collection, both mental health centers have participated in extensive and similar research with the investigators leading this study. The SAB will provide input on the development of consent materials, and methods of communication, making sure that they are appealing. The process of utilizing e-consent will be convenient and streamlined for Tier 3 participants. Additionally, participant incentives are proposed, in the amount of \$20 per parent assessment battery, and a token of appreciation for each student assessment battery to incentivize participation.

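### Parent leaders paid to promote the study work only in Partnership schools, which adds encouragement to consent in one arm, and no check on consent by arm is planned

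*Combined protocol and SAP*

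**What the plan says.** **Who promotes the study.** The relevant paragraph of Engagement in Conducting the Study opens with "For the Partnership condition, two family advocates serving on the SAB" and covers "selected parent leaders from each of the 11 schools". It then states: "Parent leaders will be compensated for the time spent to collaborate with fellow parents and school staff to communicate about and promote the study". The same sentence goes on to name outreach to minority families about access to services as an additional task.

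**Where parent leaders work.** The Partnership intervention section says "In each of the 11 Partnership schools, a parent leader, and school-employed mental health professional" will be assigned to work with the clinician and implementation team. The section on family-school-mental health partnerships again refers to a "parent leader at each of the 11 Partnership schools". The only parent-leader activity that covers all 22 schools is presenting findings in Year 5 (Dissemination and Implementation Potential).

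**How students are recruited in both arms.** Those already in treatment or newly referred "will be eligible to participate and recruited by their SBH clinician". Parents receive $20 per assessment battery, and there is "a token of appreciation for each student assessment battery to incentivize participation". Study consent is built into the clinician's consent-for-treatment process.

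**Expected numbers.** Of 4,000 students expected to have mental health challenges, "the research team estimates that 30% will consent to participate representing the recruitment goal of 1,225 students". Protection of Human Subjects projects about 612 in each condition.

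**Outcomes.** Aim 1 concerns the number of students and families receiving services, and their satisfaction. Session data are to be collected per student, but the plan does not say whether that means all Tier 3 students or only those who consent. The CSQ-8 is collected at three months or case closure, not at intake.

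**The concern.** Outreach about services is part of the Partnership intervention, and any effect it has on who seeks care belongs to the treatment effect. Promotion of the study is different. It is a research recruitment activity, and the plan lists it as a separate task. Placed in one arm of a cluster trial in which students enrol after their school has been assigned, it can change how many families consent and which ones.

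If Aim 1 counted enrolled students, extra consent would look like extra service receipt. The satisfaction comparison would rest on two groups that came in through different recruitment processes, with no baseline to reveal or correct the difference. I found no planned report of eligible, approached and consented students by arm, and no planned comparison of consented students' intake characteristics by arm.

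**Working it through.** **1. Reproduce the recruitment figure.** Inputs are from the Recruitment Plan and Protection of Human Subjects.

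- 20,000 students × 0.20 = 4,000.
- 4,000 × 0.30 = 1,200, against the stated 1,225 (25/1,225 = 2.0% apart). The stated goal implies 1,225/4,000 = 30.6%.
- 1,225/2 = 612.5 per arm, matching the stated 612.

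The plan therefore assumes one consent rate and equal arms.

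**2. Illustrate an unequal consent rate.** Assume 2,000 eligible per arm, identical service receipt and 30.6% consent in Wellness. The Partnership rates are assumptions.

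| Partnership consent | Partnership enrolled | Wellness enrolled | Ratio |
|---|---|---|---|
| 33% | 660 | 612 | 1.08 |
| 35% | 700 | 612 | 1.14 |
| 40% | 800 | 612 | 1.31 |

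**3. What an enrolled count can show.** Only students in treatment or newly referred can be recruited, so enrolled = eligible × proportion reaching treatment × proportion of those consenting. With equal eligible numbers,

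enrolment ratio = (ratio of reaching treatment) × (ratio of consenting).

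The first factor is what Partnership is meant to change. The second is what study promotion may change. Without counts of students treated and approached, the two cannot be separated.

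**4. Shift in the mean of a consented-sample outcome.** Use a normal selection model: shift = r × [λ(0.306) − λ(c)], where c is Partnership consent, λ(c) = φ(z)/c, z is the normal quantile at 1 − c, and r is an assumed correlation (0.1 to 0.5) between willingness to consent and the outcome.

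- c = 35%: 0.009 to 0.044 SD.
- c = 40%: 0.018 to 0.090 SD.

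A simple mixture agrees. If the extra consenters differ by an assumed 0.2-0.3 SD, the shift runs from (88/700) × 0.2 = 0.025 to (188/800) × 0.3 = 0.071 SD. The stated minimum detectable effect size is 0.29 (Power considerations).

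**5. Which outcomes are exposed.**

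- *Aim 1 count:* exposed if it is based on enrolled students, which the plan leaves open.
- *CSQ-8:* exposed, and it has no baseline.
- *Other Tier 3 outcomes:* analysed as difference scores, which subtract a pure intake shift. Different expected change among the extra consenters would remain.
- *Aim 2a:* school-wide records collected without consent, so unaffected.

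**The case against.** The strongest reply is that the sections describing recruitment, consent and recruitment personnel give parent leaders no part. Clinicians recruit, incentives carry no arm restriction, and consent is tied to treatment consent in every school. Promoting the study in a Partnership school could largely mean promoting the programme. The documents give no consent rate by arm, and difference scores were chosen to cope with unequal groups.

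Most of this stands, and it rules out three stronger readings that a reader might infer.

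- *Consent is encouraged in one arm and not the other.* The documents contradict this, because clinician recruitment and incentives apply in both arms.
- *The arms do differ in enrolment.* Nothing in the documents shows this. Equal arms are projected, so a difference is a risk, not a finding.
- *A rise from 30% to 35-40% would be pure recruitment effect.* The 4,000 comes from a prevalence estimate, so the 30% mixes reaching treatment with agreeing to research. A higher figure in Partnership could partly or wholly reflect the intended effect on services.

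The reply does not remove the core. The plan names promotion of the study as a paid task separate from service outreach, places it in one arm, and assigns the parent leader to work with the clinician who recruits. Difference scores cannot help satisfaction, and they do nothing for a count.

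**Conclusion.** The plan as written adds a recruitment influence in one arm, after school randomisation, with no safeguard against unequal consent. The consequence is a risk of unknown size. It could be material for an Aim 1 count of enrolled students: 14-31% in the illustration, which assumes 2,000 eligible per arm, identical services and 35-40% Partnership consent against 30.6%. The shift in means is small under the assumed inputs, about 0.01-0.09 SD against a minimum detectable effect of 0.29. Satisfaction is the outcome for which even a small shift can be neither seen nor subtracted. The point does not reach Aim 2a, and it does not show that the difference-score analyses are biased.

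**What to change.** 1. **Aim 1 count.** State that it is taken from clinician service and productivity records, already monitored under Assuring and Monitoring Intervention Fidelity, for all Tier 3 students and not from study enrolment. Confirm that these records cover students outside the study and that approvals allow counts to be used.
2. **Consent by arm.** Report eligible, approached and consented students by arm and school, and compare consented students' intake characteristics by arm.
3. **Satisfaction.** Adjust the CSQ-8 comparison for intake measures already collected, such as the Brief Problem Checklist and the social functioning scale, and show the unadjusted result beside it. Adjustment handles only measured differences.
4. **Any remaining recruitment.** Limit parent leaders to outreach about services, or give identical study information in both arms. The plan was revised in May 2023 and enrolment was to end in June 2023, so this step may change little.

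The cost is a little more analysis and reporting, and slightly slower Partnership enrolment if any remains.
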